# G. Data Analysis Plan:

**For specific aim 1**, data across conditions among CF-LVAD patients (ie, CS-lead ON v. OFF) will be compared using repeated measures analysis of variance (ANOVA) with Bonferroni *post-hoc* tests for multiple comparisons. Linear mixed modeling with random effects will be used to account for the variability in hemodynamics (e.g. heart rate, blood pressure, cardiac output) that occur during pump speed adjustments and during progressive stages of exercise (rest, mild, moderate and peak exercise). Comparisons between healthy controls and CF-LVAD patients will be compared using the Mann Whitney U test. All statistical analyses will be

performed using a computer-based analysis system (SAS, V9.4, Cary NC, USA). A P value < 0.05 will be considered statistically significant.

**For specific aim 2**, data across conditions among CF-LVAD patients (CS-lead ON v. OFF) will be compared using a two-way repeated measures ANOVA, to determine the impact of CS-lead pacing and LVAD pump speed on RV performance, and the impact of CS-lead and exercise on RV performance, with Bonferroni *post-hoc* tests for multiple comparisons. Linear mixed modeling with random effects will be used to account for the variability in parameters of RV function (dp/dt, tau, ESPVR, EDPVR, and PV area). Comparisons between healthy controls and CF-LVAD patients will be compared using the Mann Whitney U test. All statistical analyses will be performed using a computer-based analysis system (SAS, V9.4, Cary NC, USA). A P value < 0.05 will be considered statistically significant.

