# **IV. Research Methods:**

# A. Outcome Measure(s):

**For specific Aim 1:** The primary outcome will be the difference in Qc (inert rebreathing) and peak VO2 between CS-lead ON v. OFF. Secondary measures include vital signs including HR and BP, as well as 6-minute hall walk test, 10 minute gait speed test, and quality of life measures (Kansas City Cardiomyopathy Questionnaire and Minnesota Living with Heart Failure Questionnaire), all compared between CS-lead ON v. OFF.

**For Specific Aim 2:** The primary outcome will be the pressure-volume (PV) area as measured by Millar catheterization – this data variable is a direct marker of "how hard" the RV must work in the face of changes in preload (venous return). Secondary outcomes include: end-systolic pressure volume relationship (ESPVR), which assesses changes in contractility, end-diastolic pressure volume relationship (EDPVR), which assesses ventricular compliance during the diastolic portion of the cardiac cycle, dp/dt (increase in ventricular pressure during isovolemic contraction period), and tau (measure of isovolemic relaxation of the ventricle). All of these variables will be assessed during changes in LVAD pump speed, and during exercise testing (on visits 1-2, see figure 2 below) with CS-lead ON v. OFF.

- B. Description of Population to be Enrolled for completion of specific aims 1-2:
- 15 patients with advanced HF who have already undergone CF-LVAD implantation. Inclusion criteria: 1) advanced HF patients who have already received CF-LVADs and are clinically stable, ambulatory outpatients and are fully recovered (at least 3 months) from LVAD implantationExclusion criteria: 1) individuals with clinical RV failure under resting conditions, defined as moderate-severely reduced RV systolic function on echocardiography, or clinical evidence of RV failure (elevated jugular venous pressures, 3 or 4+ [significant] peripheral edema); 2) disorders that adversely influence exercise ability (e.g. arthritis, peripheral vascular disease, pulmonary disease)

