### Power Analysis:

For specific aim 1-2, based on pilot data, assuming an increase in resting Qc of 0.6Lmin following activation of CRT (coronary-sinus [CS] lead enabled [CS-ON], with a standard deviation of 0.2L/min, a sample size of 15 patients will provide greater than 90% power to detect a difference in Qc using an alpha of 0.05. Assuming an increase in right atrial pressure of ~15mmHg from rest to peak exercise (based on pilot data), a sample size of 15 patients will provide greater than 90% power to detect a difference in right atrial pressure of ~15mmHg from rest to peak exercise (based on pilot data), a sample size of 15 patients will provide greater than 90% power to detect a difference in right sided pressures from rest to peak exercise, using an alpha =0.05.

For healthy controls, based on available data previously described in the literature, assuming a reduction in RV relaxation time by 50msec from rest to exercise, a sample size of 10 patients will provide greater than 90% power to detect a difference in ventricular performance from rest to peak exercise, assuming a standard deviation of ~20msec and an alpha = 0.05.

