### Study Design and Research Methods

An overview of the study protocol is displayed in figure 2. For completion of aim 1 (testing the effect of the coronary sinus [CS] lead on functional capacity. CF-LVAD patients who have a CRT-D device will complete visits 1-2 as detailed in figure 2 and in the protocol description below. For completion of aim 2, CF-LVAD patients who do not have a CRT-D will complete visit 1 only. For CF-LVAD patients with CRT-D, the study protocol will involve a double-blinded randomized crossover design. Immediately following enrollment, CF-LVAD subjects will be randomized in a double-blind, 1:1 fashion to cardiac pacing with the coronary sinus (CS) lead enabled or disabled (CS-ON v. CS-OFF). The pacing mode will be either VVI-R or DDD-R with a backup pacing rate set at 60bpm. After four weeks, patients will return for visit 1 testing. On completion of testing, cardiac pacing will be switched (CS-ON to CS-OFF, or vice-versa) for four weeks, following which patients will return for visit 2 testing, which is identical to visit 1 testing. In this manner, all subjects will complete testing with the CS-lead ON and the CS-lead OFF; subjects will serve as their own controls to determine the impact that CRT-D pacing has on cardiovascular function and exercise performance. Following completion of visit 2 testing, the study will be completed and original CRT-D device settings returned to baseline. Computerized randomization will be performed in a 1.1 ratio to a CS-lead ON v. OFF pacing strategy - this process will be completed and recorded by a study coordinator who does not have access to the data recorded throughout the study; neither the patient nor the PI will be aware of randomization status during testing. Pacemaker settings will be adjusted by an electrophysiologist who is part of the study group but does not have access to data being collected (to ensure that blinding is maintained).

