## E. Potential Scientific Problems:

1)Recruitment of subjects for testing: The University of Colorado has an active heart failure and LVAD program, with approximately 50 CF-LVADs inserted in 2015 and over 70 patients followed in the advanced heart failure center. There are currently 37 CF-LVAD patients with CRT-D devices that are being followed clinically by the advanced heart failure and electrophysiology programs here at the University of Colorado. Thus, we do not anticipate any difficulty recruiting subjects for this proposal. Healthy volunteers will be recruited by posting flyers around the University of Colorado Anschutz Medical Campus. We will plan to enroll 30 participants with the anticipation that there will be a few dropouts (no more than 5 anticipated).

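### The Aim 1 CS-lead ON v. OFF analysis names no period (visit) term for the two-period crossover

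*Combined protocol and SAP*

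**What the plan says.** Study Design and Research Methods sets out a double-blind randomised crossover for patients who have a CRT-D. They are randomised to one setting and tested at visit 1 after four weeks; then "cardiac pacing will be switched (CS-ON to CS-OFF, or vice-versa) for four weeks", and they are tested again at visit 2. On allocation the section says "Computerized randomization will be performed in a 1.1 ratio to a CS-lead ON v. OFF pacing strategy" and mentions no blocking. It adds that "CF-LVAD patients who do not have a CRT-D will complete visit 1 only", so the number entering the crossover is not fixed.

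Section A gives the Aim 1 endpoint: "The primary outcome will be the difference in Qc (inert rebreathing) and peak VO2 between CS-lead ON v. OFF". The Power Analysis covers resting Qc only, "assuming an increase in resting Qc of 0.6Lmin following activation of CRT", with an SD of 0.2 L/min, 15 patients and power above 90%.

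For Aim 1, section G says "data across conditions among CF-LVAD patients (ie, CS-lead ON v. OFF) will be compared using repeated measures analysis of variance (ANOVA", followed by Bonferroni post-hoc tests. It adds a linear mixed model with random effects, whose stated purpose is to handle "variability in hemodynamics (e.g. heart rate, blood pressure, cardiac output) that occur during pump speed adjustments and during progressive stages of exercise". Pump speed and exercise stage both vary within a visit. No section names a term for period, visit or sequence.

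**The concern.** In this design each patient's ON-OFF difference is also a difference between two visits. Using patients as their own controls removes differences between patients but not differences between visits. Visit 2 repeats the visit 1 testing, including maximal exercise and the hall walk, so some change with repetition is plausible, though the documents give no size for it.

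A visit shift enters the ON-OFF difference with opposite signs in the two sequences. An analysis by condition alone treats that as noise, which widens the interval. If the sequences are unequal, part of the shift is also counted as pacing effect. At stake are the precision and accuracy of the reported effect and, for an outcome with less reserve than resting Qc, power. If the term is not named in advance, adjusting for period also becomes a choice made after the data are seen.

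**Working it through.** **Inputs.** From the Power Analysis: effect 0.6 L/min, SD 0.2 L/min, n = 15, alpha 0.05 (taken as two-sided). The SD is read as that of the paired difference. The visit shift π (visit 2 minus visit 1) is not in the documents and is shown as a range.

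**The plan's own figure.** A paired t-test with n = 15 and effect/SD = 0.6/0.2 = 3 has power above 99.9%. If 0.2 is instead the SD of each condition with zero correlation (SD of the difference 0.283), power is still above 99.9%. The stated figure of more than 90% is consistent with this.

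**Effect of a shift.** With true effect δ, the ON-OFF difference has mean δ + π in OFF-first patients and δ − π in ON-first patients. With n₁ and n₂ patients per sequence and no period term:

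- the estimate moves by π × (n OFF-first − n ON-first)/n;
- the variance of the differences rises by π² × 4n₁n₂/[n(n−1)], which is 224/210 = 1.07π² at 8:7 and 200/210 = 0.95π² at 10:5.

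With the term, the estimate is the mean of the two sequence means. It does not move with π, and its variance uses the pooled within-sequence SD on n − 2 df.

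**Resting Qc, 8:7.** The half-width without the term is 2.145 × √(0.04 + 1.07π²)/√15. With the term it is 2.160 × 0.2 × ½√(1/8 + 1/7) = 0.11.

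| Shift (L/min) | Half-width without term | Half-width with term | Movement at 8:7 (π/15) | Movement at 10:5 (π/3) |
|---|---|---|---|---|
| 0 | 0.11 | 0.11 | 0 | 0 |
| 0.1 | 0.12 | 0.11 | 0.007 | 0.03 |
| 0.2 | 0.16 | 0.11 | 0.013 | 0.07 |
| 0.3 | 0.20 | 0.11 | 0.02 | 0.10 |

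Power is about 100% in every row, with or without the term.

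**Likely splits.** If all 15 cross over, equal sequences are impossible. Under simple 1:1 randomisation (an assumption), a split of 10:5 or worse has probability 0.302, and 11:4 or worse 0.118.

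**Peak VO2.** No effect or SD is stated, so take an illustrative effect of 0.9 SD of the difference, which has about 90% power at n = 15. Power at 8:7, from 100,000 simulations per cell (exact noncentral t at zero shift):

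| Shift (SD) | Without term, by direction of shift | With term |
|---|---|---|
| 0 | 90% | 89% |
| 0.25 | 88-90% | 89% |
| 0.5 | 82-87% | 90% |
| 1.0 | 56-73% | 89% |

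**Fewer completers.** Section E says "There are currently 37 CF-LVAD patients with CRT-D devices that are being followed clinically", out of more than 70 patients. As an illustration only, 15 × 37/70 = 7.9, or about 8 patients. At 4:4, power without v. with the term is 59% v. 57% (no shift), 57% v. 57% (0.25 SD), 49% v. 57% (0.5 SD) and 26% v. 57% (1.0 SD).

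**Type I error.** Averaged over unblocked splits of 15, it is 5.0-5.1% without the term. Given the realised split it can differ: with a 1.0 SD shift it is about 0.8% at 8:7 and 17% at 11:4, against 5% with the term.

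**The case against.** No stated figure is wrong. Resting Qc is the only Aim 1 outcome with planning inputs, and its power is untouched by any moderate shift. Averaged over randomisation, the estimate is unbiased and type I error is held. Every loss shown depends on an assumed shift. Patients are stable outpatients at least three months after implantation, with equal periods, identical visits and blinding. A shift of 1.0 SD is therefore extreme, and at 0.25 SD the term makes almost no difference at 8:7. The peak VO2 result adds an assumed effect to an assumed shift. The eight-completer case applies the clinic's device mix to a trial that could recruit CRT-D patients preferentially. The mixed model already in section G could carry a period term. Without blocking, the term costs power on average when the shift is below about 0.3 SD.

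Most of this stands, and it limits the weight of the point. It does not remove the gap: the trial will be analysed on one realised split, not on the average over splits, and nothing in the plan says that the mixed model will include period.

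**Conclusion.** The point holds, as a low-cost improvement rather than an error in the stated power. The design is a two-period crossover and the planned Aim 1 contrast ignores period. For resting Qc the exposure is in the interval and the estimate: at an assumed 0.3 L/min shift, the half-width is 0.20 instead of 0.11 L/min at 8:7, and the estimate moves by 0.10 L/min at 10:5, in either direction. For an outcome with about 90% power and no reserve, the loss at 8:7 is negligible at a 0.25 SD shift, about 2 to 8 points at 0.5 SD, and about 16 to 33 points at the extreme of 1.0 SD. These sizes rest on assumed shifts, on 0.2 L/min being the SD of the difference, and on 15 patients crossing over, which is an upper assumption.

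**What to change.** In section G, define the Aim 1 contrast as a linear mixed model with fixed effects for CS-lead setting, period (visit 1 or 2) and sequence, a random patient effect, and exercise stage or pump speed where measurements repeat within a visit. Report the period-adjusted ON-OFF difference with its 95% CI. The period term does the work; with complete pairs, the sequence term leaves the within-patient contrast unchanged.

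State how many CRT-D patients are expected to complete both visits. If enrolment is still open, generate the sequence list among CRT-D patients in permuted blocks.

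The cost is a sentence or two in the plan, a block setting and one degree of freedom. With no shift and a 0.9 SD effect, the term costs about 0.5 points of power at 8:7, 4 at 10:5, 9 at 11:4 and 2 at 4:4. Averaged over unblocked splits of 15, power without v. with the term is 90% v. 87% (no shift), 88% v. 87% (0.25 SD), 83% v. 87% (0.5 SD) and 62% v. 87% (1.0 SD). The term therefore pays best when combined with blocking.

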#### COMIRB Protocol

COLORADO MULTIPLE INSTITUTIONAL REVIEW BOARD [name] [contact] [contact]

Protocol #: 17-1042

 Project Title: Randomized interventiOn of Biventricular pacemaker function on ventricular function among patients with mechaNical circulatory support devices: "ROBIN"

 Principal Investigator:
 [name] [name]

 Version Date: 4/24/2019

I. Hypotheses and Specific Aims:

- Specific Aim 1: Determine how cardiac-resynchronization therapy (CRT) influences ventricular performance at rest and during activity/exercise in patients with CF-LVADs. Hypothesis 1: Cardiac output (Qc) and functional capacity are higher with CRT-pacing enabled, as opposed to conventional treatment with CRT-pacing disabled.
- Specific Aim 2: Determine how the right ventricle (RV) functions at rest and during exercise among patients with CF-LVADs. Hypothesis 2A: During resting conditions, adjustments of the CF-LVAD pump speed will alter venous return of blood to the heart, causing RV workload to increase and decrease in response to increases and decreases in pump speed, respectively. Hypothesis 2B: During exercise, progressive increases in venous return will increase RV workload and limit the patient's ability to exercise.

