The testing protocol for visits 1-2 will involve two parts: Part A, and Part B, which will be completed following right heart catheterization. Part A involves LVAD pump speed adjustments at rest in the supine position. Part B involves submaximal and symptom-limited (maximal) exercise. Exercise will be performed using a stationary cycle ergometer. For Part A, measurements will include the following: HR, BP by arterial line, LVAD parameters (from LVAD monitor), pressure-volume loops from the Millar catheter and Qc (inert rebreathing). Echocardiography will be used during pump speed adjustments to assess parameters such as LV and RV systolic and end-diastolic volumes, septal position, and mitral/tricuspid regurgitant flow. For Part B, measurements obtained will include the following: HR, BP by arterial line, respiratory rate, Qc (inert rebreathing), LVAD parameters (flow, rotor speed, pulsatility index and power), echocardiography may be used to estimate flow through the LVAD and left ventricular outflow tract of the native heart), VO2, VCO2 by gas exchange, RPE and measurements outlined above from the Millar catheter (e.g. dp/dt, tau, ESPVR, EDPVR and pressure-volume area). A complete blood count (CBC) will be obtained at rest, prior to initiation of exercise. A CBC is necessary to obtain hemoglobin/hematocrit levels, which are used to further assess VO2 and other cardiac parameters (e.g. cardiac output). Notably, this blood sample will be obtained from the catheter that is placed for invasive hemodynamic monitoring - no additional catheters or peripheral IV's are required. Blood (venous and/or arterial) oxygen saturation levels will be drawn at rest and during each stage of exercise by removing a small amount of blood (approximately 1-2cc) from the catheters (arterial catheter will be used to check arterial oxygen saturation. Millar catheter will be used to check venous oxygen saturation level). Blood oxygen levels are necessary to determine oxygen consumption by exercising muscle. Cerebral and peripheral (musculoskeletal) oxygen uptake may be monitored noninvasively by NIRS. End-tidal carbon dioxide will be monitored by nasal capnography. Brain blood flow may be measured by transcranial Doppler ultrasonography.

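### Hypothesis 2A predicts that RV workload rises and falls with pump speed, but no slope or trend test is named for it, and the unordered ANOVA that is named has less power for a linear response and does not show direction by itself

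*Combined protocol and SAP*

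**What the plan says.** Section I (Hypotheses and Specific Aims) states Hypothesis 2A for resting conditions. Changing pump speed alters venous return, "causing RV workload to increase and decrease in response to increases and decreases in pump speed, respectively". That is an ordered, signed prediction.

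Section IV.A (Outcome Measures) says for Aim 2: "The primary outcome will be the pressure-volume (PV) area as measured by Millar catheterization". It describes PV area as the direct marker of how hard the RV works.

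Under Study Design and Research Methods, "Part A involves LVAD pump speed adjustments at rest in the supine position". The number, size and spacing of the speed steps are not given.

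Section G (Data Analysis Plan), Aim 2, has three elements:

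- a "two-way repeated measures ANOVA, to determine the impact of CS-lead pacing and LVAD pump speed on RV performance", and likewise for CS-lead and exercise, "with Bonferroni *post-hoc* tests for multiple comparisons";
- linear mixed modelling with random effects, which "will be used to account for the variability in parameters of RV function (dp/dt, tau, ESPVR, EDPVR, and PV area");
- the threshold: "A P value < 0.05 will be considered statistically significant". Sidedness is not stated.

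No linear contrast or slope is named. The plan does not say whether speed is numeric or categorical in the mixed model, or which of the two models decides Hypothesis 2A.

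**The concern.** A repeated measures ANOVA treats pump speeds as labels. Its F test asks whether any mean differs from the others, and it gives the same answer if the speeds are shuffled. Hypothesis 2A asks a narrower question: does PV area go up with speed? Two things follow.

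- **Power.** With three or more speeds, the F test spreads its sensitivity over k−1 degrees of freedom, while a linear response lies on one. The Bonferroni pairs, which do carry a sign, pay for every pair tested.
- **Interpretation.** A significant F is compatible with a rise, a fall or a U-shape. If the report gives the F test as the result for 2A, the reader cannot tell which of these occurred.

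The mixed model could answer the directional question. Because its form and role are open, the choice between the models, and the coding of speed, could be made after the data are seen.

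**Working it through.** **The plan's own figures.** The Power Analysis gives none for PV area against pump speed. Its first figure concerns Qc: difference 0.6 L/min, SD 0.2, 15 patients. Taking 0.2 as the SD of differences, the noncentrality is (0.6/0.2)×√15 = 11.6 and paired-t power exceeds 99.9%, so the stated figure of more than 90% is met. It does not bear on Hypothesis 2A.

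**Inputs.** From the documents: "15 patients with advanced HF who have already undergone CF-LVAD implantation", and alpha 0.05 (two-sided assumed). My assumptions:

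- k = 3 to 5 equally spaced speeds. Both raising and lowering speed implies at least three levels; two is shown for reference.
- Linear response, sphericity, within-patient residual SD 1, and all 15 patients contributing to a one-factor model.

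**Step 1: size the effect.** With centred speed scores x and slope b, the noncentrality of the linear contrast is λ = n·b²·Σx². I choose b so that the two-sided slope test on 14(k−1) df has 80% power. For k = 3, Σx² = 2 and b = 0.530, so λ = 15 × 0.530² × 2 ≈ 8.42. For k = 4 and 5, λ = 8.22 and 8.13.

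**Step 2: omnibus F.** The same λ is spread over k−1 numerator df, with 14(k−1) denominator df.

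**Step 3: Bonferroni, lowest v. highest speed.** The squared noncentrality is n·[b(k−1)]²/2, tested at 0.05 divided by k(k−1)/2 on the same pooled error. For k = 5: 15 × (4 × 0.233)²/2 ≈ 6.5, at alpha 0.05/10 = 0.005.

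**Step 4: a more cautious slope test.** If the random effects include patient-specific slopes, the slope is tested on about 14 df. The same λ is used.

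| Speeds (k) | Slope, pooled df | Slope, 14 df | Omnibus F | Bonferroni lowest v. highest | N for F to reach 80% |
|---|---|---|---|---|---|
| 2 | 80% | 80% | 80% | 80% | 15 |
| 3 | 80% | 77% | 69% | 64% | 19 |
| 4 | 80% | 76% | 62% | 49% | 22 |
| 5 | 80% | 76% | 57% | 36% | 24 |

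**Step 5: direction.** 20,000 simulated trials per pattern at k = 3, with the same range of means as in step 1:

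| True pattern | F significant | Upward slope significant | Any upward Bonferroni pair significant |
|---|---|---|---|
| Rise (as 2A) | 69% | 80% | 67% |
| Full reversal | 69% | 0% | 0% |
| U or inverted U | 81–82% | under 3% | 64% |

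**Step 6: where the slope does worse.** If only the top of five speeds differs, by the same range, F has 69% power and the slope test about 60%.

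**The case against.** Four points can be made for the plan.

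- **The mixed model is already there.** It covers PV area and could carry a slope. A reader might infer that the plan can test 2A only with unordered categories. The documents do not support that: unordered coding is established for the ANOVA only. What stands is that the model's fixed effects, its coding of speed and its role in testing 2A are not stated.
- **The pairs have signs.** A reader might infer that Aim 2 could be declared positive on a response running the wrong way. The documents nowhere say that a significant F alone supports 2A, and step 5 shows that signed pairs expose a full reversal. They do not reliably expose a U-shape, and the plan does not say which pairs decide. A two-sided slope test without a sign rule would also be significant for a fall.
- **The loss can be made to look larger.** Testing the extreme pair on its own 14 df gives 58%, 40% and 27%, but that compares it with a slope and an F on pooled error. Like for like it is 64%, 49% and 36%. Counting any upward pair at three speeds gives 67%.
- **The inputs are assumed.** The number and spacing of speeds and the PV-area SD are absent, and the planned analysis has two factors. Patients without a CRT-D complete visit 1 only and have no ON/OFF factor, so a complete two-way ANOVA would use fewer than 15 patients if any such patients are among them.

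ANOVA with corrected pairs is a standard and valid analysis. The point is that a better-matched test of 2A is available on the same data.

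**Conclusion.** The point holds in a limited form. Hypothesis 2A is directional, the test tied to pump speed is not, and the mixed model that could close the gap is not assigned to it.

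Against a linear response, with 15 patients and sphericity, the F test falls short of a pooled-error slope test by 11, 18 and 23 percentage points at 3, 4 and 5 speeds (80 minus 69, 62 and 57). If the slope is tested on 14 df, the gap is about 8, 14 and 18 to 19 points. It is nil at two speeds and can reverse for a threshold response. Because the documents do not fix the number of speeds, no single figure can be given.

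On interpretation, a significant F alone does not establish the predicted direction. Signed pairs repair this for a full reversal, but not dependably for a non-monotone pattern.

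This is a cheap improvement to the specification, not a flaw that invalidates the analysis.

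**What to change.** In section G, under Aim 2, name one primary test of Hypothesis 2A: the slope of PV area on pump-speed step, coded as change from the patient's own clinical speed, from the linear mixed model already planned. Also state:

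- the estimate with its 95% CI, at two-sided alpha 0.05;
- the sign rule: 2A is supported only if the slope is significant and positive;
- the fixed and random effects, and how speed steps are coded;
- how pacing status enters for patients without a CRT-D, so that those with visit 1 only contribute to the slope.

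Keep the omnibus F and the Bonferroni pairs as supporting checks of shape.

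The cost is SAP wording, with no new data or visits. The downside is that a non-monotone or threshold response would be picked up mainly by the supporting tests. It is small for monotone shapes: where F has 80% power against the monotone step pattern least favourable to the slope, the linear test still has 78%, 75% and 71% at 3, 4 and 5 speeds.
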